Aim 1: Determine the influence of menthol flavoring on smoking reinforcement in the context of a reduced nicotine standard in the laboratory. Abstinent smokers (> 12 hours) will attend four laboratory visits. Following a 7-day baseline period of usual brand smoking at home, smoking session 1 will measure reinforcement of one's usual brand cigarette via ad-libitum smoking, where subjective response (satisfaction, craving reduction, psychological reward, sensory effects like throat hit), smoking exposure (CO boost), and behavior (number of puffs, puff volume) will be measured. Following smoking session 1, participants will then undergo two experimental conditions (counterbalanced) in their home environment and the lab for 7 days each: (1) 7 days smoking menthol VLNCs; (2) 7 days smoking non-menthol VLNCs. Participants will be instructed to switch their usual cigarette for the assigned cigarette for each 7-day period (allowing for other product use during that time without specific instruction to model real world behavior). Each condition will be separated by a 7-day wash-out period. On the last day of each condition (smoking Visits 2 and 3), participants will smoke the assigned research cigarette in the laboratory, and data on subjective response, smoking exposure, and behavior will be measured. Hypothesis: Craving reduction and positive subjective response will be greater for menthol VLNCs compared to non-menthol VLNCs, but lower compared to usual brand.

Aim 2: Determine the influence of menthol flavoring on smoking reinforcement in the context of a reduced nicotine standard in the natural environment. During each 7-day period of exposure, participants will complete assessments of cigarette and other tobacco use, withdrawal, and subjective response (satisfaction, craving reduction, reward, sensory effects) via twice-daily EMA. Hypothesis: Cigarettes per day, craving reduction, and positive subjective response will be greater for menthol versus non-menthol VLNCs, but lower compared to usual brand. Per previous work, ATP use will be greater in both VLNC conditions compared to usual brand. Effects of menthol vs non-menthol VLNCs on withdrawal, mood, cigarette compliance, and ATP will be compared.

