Smoking Session 1 (V2): Usual Brand Smoking. At the end of the 7-day baseline period of usual brand smoking, > 12-hour abstinent smokers (expired CO \leq 6ppm) or >50% reduction in CO from baseline, per Co-I [name] research²⁴ will return to the laboratory to assess absolute reinforcing value (ARV) of their usual brand cigarette by having participants smoke one of their usual brand cigarettes (ad libitum) through a transducer-based smoking topography data collection device. The instrument records puff volume, duration and velocity and inter-puff interval for each puff and their aggregate averages. These puff topography measures are useful indices of smoke exposure and are sensitive to differences in smoking behavior that may occur between different cigarette flavoring types.^{59,61,124} Puff topography measures will be used to examine whether increased puff volume, duration, and lower inter-puff interval differ across cigarettes as a measure of compensation. Prior to smoking participants will be asked when they smoked their last cigarette. Immediately before and after smoking the following measurements will be taken: heart rate and blood pressure will be assessed (heart rate, but not blood pressure, will be collected for remote sessions), and exhaled carbon monoxide (CO boost).

Subjective response to smoking (craving reduction, psychological reward, satisfaction, sensory effects) using the **Modified Cigarette Evaluation Questionnaire (mCEQ)**¹³⁸⁻¹⁴⁰ in addition to the **Nicotine Drug Effects Questionnaire (N-DEQ)**, the **Duke Sensory Questionnaire (DSQ)**, and the **Minnesota Nicotine Withdrawal Scale (MNWS)** will be measured immediately after smoking. Exhaled CO will be collected via a Smokerlyzer CO detector (Bedfont Scientific LTD), and measured in ppm immediately before and 10 minutes after smoking. CO boost has been used in previous studies^{141,142,143} to index smoke exposure, and will be calculated as the difference between pre- and post-smoking levels.

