At the end of V2, participants will receive the first set of assigned research cigarettes and will be asked to smoke those cigarettes in their home environment for 7 days; starting on the day after V2. The ordering of flavor of the research VLNCs to be smoked (menthol and non-menthol) will be counterbalanced and assigned prior to Visit 2 (Individuals who complete the session remotely will be scheduled for a pick-up date to get the VLNCs1). During each 7-day period of exposure, participants will be instructed to switch their usual brand cigarette for the assigned research cigarette and will provide daily data on smoking quantity, craving, withdrawal, subjective response, and alternative tobacco product use via twice daily EMA surveys. We will allow for other tobacco product use without specific instruction to align with the real-world scenario, as these products will exist on the market even if a menthol ban and/or a reduced nicotine standard are enacted. Given the high prevalence of dual and poly-tobacco use in this age group, we will examine change in alternative tobacco product use between conditions as a secondary outcome in exploratory analyses, per Co-I [name]'s and [name]'s previous work. Participants will have a 7-day period wash-out period of return to smoking as usual (own brand of cigarette) between the experimental conditions.

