Safety: Pregnancy tests will be performed for all female participants prior to engaging in a smoking session. The suicide subscale from the Mini International Neuropsychiatric Interview (MINI)⁹ will be used to evaluate suicide risk. A licensed clinical practitioner will be available to conduct the mental health assessment (see section F). CO level will be obtained at every session to evaluate level of exposure to smoke; a large increase in CO can be a reason for withdrawing a participant from the study. **The Patient Health Questionnaire** 9-item version (PHQ-9)^{10, 11} is a widely used and validated 9-item questionnaire assessing depressive symptoms in the past 2 weeks. This measure will be used for sample description given the high co-occurrence of smoking and depression and will be used to screen out individuals with moderately severe and severe depression. **Brief Medical History** assesses physical and emotional health to establish eligibility for participation. In subsequent sessions, the **Health Changes Questionnaire** asks whether the participant experienced any changes in his/her physical or emotional health since their last visit, including whether they have visited the doctor, the hospital, or whether they have had a change in any of their medications. Any endorsement of a negative health change will be tracked as an adverse event. The **Adverse Events Questionnaire** asks about adverse events experienced since the last visit.

Past 7-day tobacco use will be measured in two different ways. First, at V2 (as part of the cigarette distribution and accountability log) past 7-day tobacco use will be comprehensively assessed using a **Timeline Follow-Back (TLFB)** technique, a reliable calendar-assisted interview validated for estimating daily use

of tobacco and other substances.¹²⁻¹⁴ The TLFB will determine: # cigarettes per day; and frequency and quantity of use of all other tobacco products at baseline to determine the number of cigarettes to be dispensed for the experimental conditions. The **7-day Tobacco Use Questionnaire** will be administered at VLNC2 pick-up (between Visits 3 and 4), where there is a 7-day wash-out period and will ask about past 7-day menthol and non-menthol cigarette smoking, frequency of use of other tobacco products, quit attempts in the past 7-days, and use of other tobacco products to quit.

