Primary Outcomes: (a) The relative reinforcing value (RRV) of usual brand cigarettes vs menthol VLNCs; (b) RRV of non-menthol VLNCs vs menthol VLNCs. RRV will be operationalized as within-subject differences in subjective ratings of cigarette appeal/reinforcement (satisfaction, reward, craving reduction, physical sensations) during each ad libitum smoking session. Secondary Outcomes: (a) CO boost; and (b) puff topography (number of menthol versus non-menthol cigarette puffs consumed, number of minutes smoked, interval between puffs).

Analysis of covariance will be conducted to examine effects of cigarette type (usual brand, menthol VLNC, non-menthol VLNC) on the outcomes of interest, controlling for cigarettes per day (CPD), nicotine dependence, race/ethnicity, gender, and age of smoking onset as potential covariates. Factors related to study drop-out and differences in cigarette compliance will also be examined as potential covariates. Exploratory analyses will examine differential reactions to usual brand and each research cigarette by race/ethnicity (White, Black, Hispanic, Other) and by gender. Significant interactions will be followed up with individual contrasts of cell means using Fisher's Least Significant Difference tests. We will examine whether topography differs as a function of in-person versus remote session.

3. EMA Analyses (Aim 2)

Primary Outcomes: (a) within-day subjective response (craving reduction, satisfaction, psychological reward, physical sensations like throat grab) to the most recent cigarette smoked; (b) within-day number of research cigarettes smoked per day; (c) within-day number of non-research cigarettes smoked; and (d) within-day withdrawal intensity. Secondary Outcomes: (a) within-day use of alternative tobacco products; (b) changes over the course of days (creating an average change score for each person) for each outcome; (c) number of days abstinent from tobacco use.

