Patterns of missing data, compliance, distributional properties of variables, and correlations among all measures will be assessed. We will control for potential variables related to missing data and utilize multiple imputation methods (expectation maximization algorithm).¹⁶⁰⁻¹⁶³ Analysis will use linear mixed modeling with random subjects effects^{164,165} to assess the main effect of cigarette type on the primary and secondary outcomes of interest. Models will use a contrast to compare differences between menthol VLNC and non-menthol VLNC at the day-level on predictions of the outcome of interest and that outcome of interest at time t (e.g., morning) predicting behavior (number of cigarettes, any smoking, craving, withdrawal) occurring at a subsequent time point (controlling for cigarette consumption from the previous report). Comparison of usual brand and the menthol VLNC ratings will also be made to determine the perceived similarity of the VLNC to one's own brand. A sub-group of respondents may have fixed (unchanging) ratings of subjective response, craving, cigarettes per day, or withdrawal over the course of 7 days, although this is unlikely given the team's previous research. We will examine baseline and daily factors that set "no changers" apart from those whose show fluctuations in these factors, and examine these as potential covariates in models. Within-person slopes capturing associations between cigarette type and the EMA outcome of interest will be saved in regression models and used to predict the ETM responses.

4. ETM Analyses (Aim 3)

Primary Outcomes: (a) consumption of alternative tobacco products (milligrams of nicotine for alternative tobacco sources) as a function of cigarette type available. Typically, as cigarette price increases, consumption of other tobacco products increases.¹⁴ Secondary Outcomes: (a) breakpoint: the first price at which consumption of the available cigarette is zero; (b) intensity of demand: consumption at the lowest price); (c) elasticity of demand: sensitivity of cigarette consumption to increases in cost, (d) Omax: maximum expenditure for cigarette type available; and (e) Pmax: price at which expenditure is maximized.

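### Usual brand is always first, so the usual-brand contrasts, one of them primary, cannot be separated from a first-session or free period effect, and no caveat or sensitivity analysis is planned

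*Combined protocol and SAP*

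**What the plan says.** **Order.** The Aim 1 text and the section on Smoking Session 1 (V2) fix usual brand as home week 1 and as the first laboratory smoking session: "Following a 7-day baseline period of usual brand smoking at home, smoking session 1 will measure reinforcement of" the participant's own brand. The V2 section places that session "At the end of the 7-day baseline period of usual brand smoking". Randomised order applies only to the research cigarettes: "The ordering of flavor of the research VLNCs to be smoked (menthol and non-menthol) will be counterbalanced and assigned prior to Visit 2".

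**Role of the contrast.** J.2 names as a primary outcome for Aim 1 "The relative reinforcing value (RRV) of usual brand cigarettes vs menthol VLNCs", next to non-menthol versus menthol VLNC. The measure is given as "RRV will be operationalized as within-subject differences in subjective ratings of cigarette appeal/reinforcement", taken at the laboratory sessions. The hypotheses of Aims 1 and 2 also place the VLNCs below usual brand. For the EMA data, J.3 adds: "Comparison of usual brand and the menthol VLNC ratings will also be made".

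**Model.** J.2 uses one analysis of covariance with a three-level cigarette-type factor, and J.3 a linear mixed model with random subject effects. Neither lists a period, visit or sequence term, or a caveat about order.

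**Wash-out.** Between the two VLNC weeks participants return to usual brand. The 7-day Tobacco Use Questionnaire "will be administered at VLNC2 pick-up (between Visits 3 and 4), where there is a 7-day wash-out period". It covers cigarettes, other tobacco products and quit attempts. No analysis of it is described.

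**The concern.** A within-person comparison with a condition that always comes first measures the product difference plus whatever else separates the first occasion from later ones. Here that could include unfamiliarity with the topography device, the novelty of EMA, and a different visit routine: the purchase tasks and the risk, predicted-behaviour and utility questionnaires are described before smoking at Visits 3 and 4, but not at Visit 2. Such an effect could run either way. It could imitate a lower rating of VLNCs, or hide a real one.

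The stake is one of the two Aim 1 primary outcomes and the policy reading built on it. The Background section argues that if VLNCs lose appeal against normal-nicotine cigarettes whatever their flavour, nicotine reduction could be effective on its own. Usual brand is the only condition in the trial that is not a VLNC, so that reading depends on the fixed-order contrast.

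**Working it through.** **The plan's own figure.** Section J.1 states power of 0.8 at n = 100. It gives no effect size, SD, alpha or sidedness, so it cannot be recomputed. The point is one of design and does not rest on it.

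**Step 1: is the contrast estimable?** Take the two sequences usual–menthol–non-menthol and usual–non-menthol–menthol, 50 participants each (total 100, from J.1), with a fixed effect per participant (100 columns), two cigarette-type columns and a time term.

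| Time term | Rank / columns | Menthol VLNC vs usual brand | Menthol vs non-menthol VLNC |
|---|---|---|---|
| none | 102 / 102 | estimable, relative variance 0.020 | 0.020 |
| first-session indicator | 102 / 103 | not estimable | 0.020 |
| categorical period | 103 / 104 | not estimable | 0.020 |
| linear, weeks 1, 2, 4 | 103 / 103 | estimable, 0.040 | 0.020 |
| linear, sessions 1, 2, 3 | 103 / 103 | estimable, 0.065 | 0.020 |

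The reason for the two failures is direct: the indicator for usual brand and the indicator for the first session are the same column.

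**Step 2: why a linear trend is different.** Let D be Visit 4 minus Visit 3, averaged over the two orders. The cigarette effect cancels, so D is pure time.

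- In calendar weeks, D spans 4 − 2 = 2 weeks. The mean VLNC week is (2 + 4)/2 = 3, which is 2 weeks after usual brand. The correction is 2/2 = 1.0 × D.
- In session numbers, D spans 3 − 2 = 1 session. The mean VLNC session is 2.5, which is 1.5 sessions after usual brand. The correction is 1.5 × D.

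With k as the multiplier and equal numbers per order, D is uncorrelated with the unadjusted contrast and both have variance 2/100 = 0.020. The adjusted variance is 0.020 × (1 + k²):

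- k = 1.0: 0.020 × 2.00 = 0.040, or 2.0 times.
- k = 1.5: 0.020 × 3.25 = 0.065, or 3.25 times.

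The effect detectable with 80% power at n = 100 (assuming a two-sided 5% test) is (1.960 + 0.842)/√100 = 0.280 SD of the paired difference. After adjustment it becomes 0.280 × √2.00 = 0.396 or 0.280 × √3.25 = 0.505.

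**Step 3: size of the inseparable part.** The documents give no figure for a first-session shift, so a range is assumed. With shift b in SDs of the paired difference, no product effect and a two-sided 5% test, P(significant) = Φ(b√n − 1.96) + Φ(−b√n − 1.96).

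| b | n = 100 (J.1) | n = 138 (section C.4) |
|---|---|---|
| 0.1 | 17% | 22% |
| 0.2 | 52% | 65% |
| 0.3 | 85% | 94% |

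A larger sample makes this worse, because the shift does not shrink with n.

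**Step 4: what the wash-out week can show.** Section 3 (duration and visits) gives 21 days of monitoring, and the compensation table gives 42 prompts: 42/2 per day = 21 days = 3 weeks, namely the baseline week and the two VLNC weeks. The wash-out week therefore has no EMA, and it has no smoking session. Only tobacco use is recorded in it. For those outcomes, a second usual-brand week would in principle make the contrast estimable with a first-week indicator (relative variance 0.020), but still not with free week effects (rank 104 of 105).

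**The case against.** The strongest reply is that the trial is about menthol. Aims 1 and 2 are both framed around the influence of menthol flavouring, and that contrast is counterbalanced and untouched. Usual brand is described as a baseline, and there is a practical reason for putting it first: section C.4.f uses consumption reported at Visit 2 to set how many research cigarettes are dispensed. J.3 makes menthol versus non-menthol its specified model contrast and adds the usual-brand comparison separately, to judge perceived similarity. Reactivity to EMA is asked about after Visit 4 and at the 30-day follow-up.

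All of this stands, and it limits the weight of the point. It does not remove it. J.2 still lists usual brand versus menthol VLNC as primary within one cigarette-type model, and no analysis uses the reactivity questionnaire.

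Two stronger readings are tempting, and the documents do not support them. A reader might infer that the contrast is wholly inseparable from time. It is not: a linear trend is estimable (step 2). A reader might also infer that a second usual-brand week has been measured and could test the primary contrast. It cannot, because that week holds no subjective ratings. Even for cigarette counts it is a weak check:

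- Participants are asked in that week to return to their baseline level of smoking.
- The week follows one VLNC week for everyone.
- The instrument differs from the Visit 2 Timeline Follow-Back, which records quantity as well as frequency of other products, while the questionnaire lists only frequency.

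**Conclusion.** The point holds in a limited form. The usual-brand contrasts (Aim 1 primary outcome (a) and the usual-brand parts of the Aim 1 and Aim 2 hypotheses) are confounded with any first-session or unrestricted period effect, and J.2 and J.3 neither say so nor plan a check. A purely linear trend can be removed, at 2.0 to 3.25 times the variance. The menthol versus non-menthol contrast is not affected.

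The estimability result follows from the design alone. The variance ratios assume complete data, equal numbers per order and equal within-person variance. The 17%, 52% and 85% figures rest on assumed shifts and a two-sided 5% test. Nothing in the documents shows that such a shift exists, or its direction, so they illustrate sensitivity and do not predict an error. The sponsor should make the change, but the trial's main menthol question does not depend on it.

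**What to change.** 1. In J.2 and J.3, label every usual-brand contrast as fixed-order. Report it apart from the counterbalanced menthol versus non-menthol contrast, and state that it is not attributed to nicotine content alone.
2. Pre-specify a sensitivity analysis with a linear trend in session or week, estimated from the VLNC crossover. For the laboratory ratings this amounts to subtracting 1.0 × (calendar weeks) to 1.5 × (session number) the Visit 4 minus Visit 3 difference averaged over orders. State the variance penalty, and state that it cannot remove a one-off first-session effect.
3. If the wash-out questionnaire is reported, present it only as a descriptive check on cigarette and other-product use, with the limits listed above. An absence of change should be called weak reassurance.

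The cost is wording in the analysis plan and one or two extra models on data already planned. No visit, procedure or cigarette assignment changes.

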Aim 3: Determine the influence of a menthol flavor ban on tobacco purchasing behavior in the context of a reduced nicotine standard using an ETM. At Visit 5, participants will complete two ETMs in the laboratory to model the impact of menthol flavoring and nicotine content on cigarette purchasing in the context of all available tobacco products currently on the market. ETM 1 will evaluate willingness to purchase and smoke non-menthol VLNCs at increasing prices under the scenarios where a

nicotine reduction policy is in effect and menthol is banned in combustible cigarettes. ETM 2 will evaluate willingness to purchase and smoke menthol vs non-menthol VLNCs at increasing prices under the scenario where a nicotine reduction policy is in effect but menthol in combustible cigarettes is available. In both ETMs, all ATPs will be available in different flavors, including menthol, to simulate the real-world marketplace. Hypothesis: In ETM 1, YAs will be more likely to choose an ATP than purchase any cigarettes. In ETM 2, YAs will be more likely to purchase menthol VLNCs or ATPs than purchase non-menthol VLNCs or no tobacco products.

Exploratory Aim: Determine the influence of a menthol flavor ban on tobacco purchase behavior when menthol is banned in all combustible tobacco products (cigarettes, cigars), but is available in non-combustible products (e.g., e-cigarettes).

The proposed research design is unlike existing research, as it combines rigorous, controlled laboratory paradigms of smoking response with “real-world” measurements of the same to determine the relative impact of menthol characteristics and nicotine on cigarette smoking in YAs, a vulnerable group of tobacco users, and adults aged 26-34, who also have high rates of menthol cigarette use. Beyond informing policy, this proposal will validate a new set of measures to be used in future studies to evaluate the potential impact of tobacco policies (e.g., a ban on all flavors) on YA cigarette and alternative tobacco use behavior.

B. Background and Significance

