At the conclusion of the laboratory and take-home phases, participants will complete two ETMs in the laboratory. The ETM will assess reinforcing value of the study cigarettes smoked by the degree to which they are willing to pay for these study cigarettes at increasing prices, when all other available tobacco products on the market are offered at a fixed price. Participants will be shown a virtual “marketplace” of combustible and non-combustible tobacco products and will be given the option to make purchases of, and take home, the products they would like to use for the week, under two policy scenarios: (1) where menthol and non-menthol VLNCs, but no NNCs or usual brand cigarettes are available in the marketplace, thus modeling a reduced nicotine standard and no menthol ban (on combustible cigarettes); and (2) where non-menthol VLNCs are available, but menthol VLNCs and NNCs or usual brand cigarettes are not available; thus modeling a reduced nicotine standard with a menthol ban on combustible cigarettes. Participants will receive account balances approximately equal to the money they would spend on a week’s worth of tobacco. In both ETMs, all alternative tobacco products will be available in menthol and other flavors that are popular. They can purchase as many or few tobacco products as their account balance allow, including no tobacco products; they can ‘save’ unspent spends. Thus we are able to model the possibility of switching and quitting behavior in response to a nicotine and menthol ban product standard. Participants will be re-contacted 30-days after the ETM visit to assess whether smoking and other tobacco use has returned to baseline levels, and cessation services will be offered.

Due to restrictions on in-person sessions because of COVID-19, virtual sessions will be offered. See section **Protocol Modifications in Response to COVID-19** below for more detail.

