C.6. Laboratory Visit 5 (V5) and ETM Procedure. Participants will complete the ATSQ, mFTQ, MNWS, and QSU after which two separate ETM³⁻⁶ tasks (counterbalanced) will be administered at the conclusion of the laboratory and take home trials (V5) to >12 hour abstinent participants. In the tasks, participants will be shown an online virtual ‘marketplace’ of cigarettes and all combustible and non-combustible tobacco products that are available on the market. Participants will be instructed to complete the task as if they were purchasing the products from a retailer, and told to make purchases of cigarettes and/or alternative tobacco products that they would take home and use for the week. The price of cigarettes will increase over eight trials (\$0.12, \$0.25, \$0.50, \$1.00, \$2.00, \$4.00, \$8.00, and \$16.00 per cigarette). The prices of alternative products available on the market will remain fixed, and will reflect the average cost of these products in Oklahoma. The first iteration of the task (ETM 1) will assess participant’s willingness to purchase non-menthol VLNCs at increasing prices, where no other types of cigarettes will be available (e.g., menthol NNCs; menthol VLNCs); this will model a scenario where a nicotine reduction policy is in effect and menthol in combustible cigarettes is banned. Findings from ETM 1 will inform FDA whether the presence of menthol-containing tobacco products, beyond cigarettes, leads to significant changes in combustible and non-combustible product use. The second iteration of the task (ETM 2) will assess participant’s willingness to purchase menthol VLNCs at increasing prices, where non-menthol VLNCs are available but no other cigarette types (e.g., NNCs) are available; this will model a nicotine reduction policy without a menthol ban. The prices for non-menthol VLNCs in ETM 1 and menthol VLNCs in ETM 2 will be presented at increasing prices. All alternative tobacco products presented in the ETMs will be available in different flavors, including menthol, to simulate the real-world marketplace.

Participants will receive account balances approximately equal to the money they spend on tobacco in one week. They will be instructed that they can ‘save’ unspent money, and purchase as many or few tobacco products as their account balance allows, including no tobacco products at all. Results of the ETM will not be actualized – meaning the ETM will be hypothetical and they will not receive

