the products in their account. Real-world brands of each product type will be presented in the ETM and chosen from those with the highest grossing product sales at the time of funding. The ETM tasks will serve as a controlled assessment of tobacco decision-making processes (e.g., alternative product use behavior) to be compared with patterns of product use generated from laboratory and EMA assessment in the field.

Participants can complete the ETMs in person or remotely, online.

The following images of tobacco/nicotine products will be shown in the ETM:

- a) SPECTRUM Study cigarettes menthol OR non-menthol flavors, depending on the ETM;
- b) Little cigars
- c) Cigarillos
- d) E-cigarettes (e.g., cigarette-like systems such as Juul and tank-like systems such as NJOY prefilled tanks)
- e) Snus;
- f) Conventional smokeless tobacco products
- g) Non-prescription medicinal nicotine (e.g., 2mg and 4mg nicotine gum; 7, 14 and 21 mg nicotine patch) menthol and regular flavors
- h) Large Cigars
- i) Hookah/shisha
- j) Tobacco free nicotine pouches

30-DAY FOLLOW-UP

A month (30-days) after the final study visit, participants will complete the smoking stages of change, mFTQ, and ATSQ before completing a third ETM in which will assess appeal for non-menthol VLNCs in the scenario where menthol is restricted in all combustible tobacco products. Thus, the only product in which menthol would be available in ETM 3 is e-cigarettes. After that, participants will complete a brief survey indicating whether smoking and other tobacco use has returned to baseline levels (**End of Study Questionnaire**). This 30-day follow-up will be offered face-to-face or remotely. at the participant's preference. They will also be provided cessation referrals.

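### ETM 1 cannot show whether the presence of menthol products beyond cigarettes changes product use, because menthol alternatives are on sale throughout ETM 1 and ETM 2

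*Combined protocol and SAP*

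**What the plan says.** The Visit 5 marketplace tasks are described in C.6, whose numbering I follow. After defining ETM 1, that section states what it is for: "Findings from ETM 1 will inform FDA whether the presence of menthol-containing tobacco products, beyond cigarettes, leads to significant changes", with combustible and non-combustible use both in view.

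The cigarettes on offer differ by task. ETM 1 measures "willingness to purchase non-menthol VLNCs at increasing prices, where no other types of cigarettes will be available". ETM 2 measures "willingness to purchase menthol VLNCs at increasing prices, where non-menthol VLNCs are available but no other cigarette types" can be bought. The cigarette price runs over eight trials, from $0.12 to $16.00.

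The alternative tobacco products (ATPs) do not differ by task. C.6 says: "All alternative tobacco products presented in the ETMs will be available in different flavors, including menthol, to simulate the real-world marketplace". Aim 3 agrees: "In both ETMs, all ATPs will be available in different flavors, including menthol, to simulate the real-world marketplace". So does the design summary in Section B: "In both ETMs, all alternative tobacco products will be available in menthol and other flavors that are popular". On price, C.6 says: "The prices of alternative products available on the market will remain fixed".

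A third task, ETM 3, is given a month after the final visit. The 30-Day Follow-up section says "the only product in which menthol would be available in ETM 3 is e-cigarettes". The Exploratory Aim in Section A describes it differently: menthol leaves combustible products and stays in non-combustible ones.

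In J.4 the primary ETM outcome is ATP consumption in milligrams of nicotine, according to which cigarette is on offer. The models then take one cigarette type at a time and predict ETM outcomes from laboratory or EMA measures. J.5 adds flavor preference by product type as an exploratory outcome.

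**The concern.** The C.6 sentence is causal in form: it asks whether the presence of one class of products leads to changes in use. That needs variation in presence. If menthol ATPs are on every menu, heavy ATP buying in ETM 1 fits several accounts: attraction to menthol ATPs, demand for ATPs in any flavor, rejection of very low nicotine cigarettes (VLNCs) in general, or habitual ATP use. ETM 1 cannot tell these apart.

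What is at stake is a conclusion addressed to a regulator. Whether menthol left in other products undoes part of a menthol cigarette ban is a different policy question from what a menthol cigarette ban does while those products remain. The Visit 5 design bears on the second question. The sentence promises the first.

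**Working it through.** The plan gives no figure to reproduce. The question is whether the effect can be estimated at all, so the check compares the menus and then asks which effects the design separates.

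**Menus, from C.6, Aim 3, Section B, the Exploratory Aim and the 30-Day Follow-up section**

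| | ETM 1 | ETM 2 | ETM 3 |
|---|---|---|---|
| Menthol VLNC on sale | no | yes | no |
| Menthol e-cigarettes | yes | yes | yes |
| Menthol combustible ATPs | yes | yes | no |
| Menthol in other non-combustibles | yes | yes | no (30-Day Follow-up) or yes (Exploratory Aim) |
| Timing | Visit 5 | Visit 5 | 30 days later |

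**ETM 1 and ETM 2.** Let C = 1 if menthol VLNCs are on sale, A = 1 if menthol ATPs are on sale, and p = the rising cigarette price. Write mean purchasing as

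b0 + b1·log(p) + b2·C + b3·A.

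- ETM 1 (C = 0, A = 1): (b0 + b3) + b1·log(p)
- ETM 2 (C = 1, A = 1): (b0 + b3 + b2) + b1·log(p)
- ETM 1 minus ETM 2 at the same p: −b2

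The menthol ATP effect b3 appears only in the sum b0 + b3. A rank check at the eight stated prices gives:

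| Data | Rows | Rank, of 4 columns | b3 estimable | b2 estimable |
|---|---|---|---|---|
| ETM 1 | 8 | 2 | no | no (C is constant) |
| ETM 1 + ETM 2 | 16 | 3 | no | yes |

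The result does not depend on this model form. A equals 1 in every row, so its column duplicates the intercept whatever other terms are added.

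**What else moves between the tasks.** The price p belongs to the non-menthol VLNC in ETM 1 and to the menthol VLNC in ETM 2. So −b2 is the effect of removing menthol VLNCs only at prices where the rest of the cigarette offer is comparable. This does not restore any variation in A.

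**Adding ETM 3.** Split A into e-cigarettes (E), combustible ATPs (K) and other non-combustibles (O), and let T mark the 30-day task.

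- ETM 1 minus ETM 3, Exploratory Aim menu: bK − bT
- ETM 1 minus ETM 3, 30-Day Follow-up menu: bK + bO − bT

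If bT is assumed to be zero, the contrast is estimable (rank 4 of 6 columns). With a time term it is not (rank 4 of 7), because ETM 3 is always the 30-day task. E equals 1 in all three tasks, so the menthol e-cigarette effect is not estimable under either menu, with or without the time term.

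**The case against.** The strongest reply is that this is a sentence of rationale on which no analysis depends. Aim 3 concerns a menthol ban in cigarettes, and its hypotheses are about choices within each marketplace. No outcome or model in J.4 or J.5 estimates an effect of menthol ATPs being present. That is right, and it limits the point to a stated inference.

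A second reply is that the sentence can be read loosely: with menthol still sold elsewhere, do people who lose menthol cigarettes move to other products? ETM 1 against ETM 2 does bear on that. If this was the meaning, rewording settles the matter. The present wording still says something else.

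A third reply is that related plans exist. J.5 already looks at flavor preference by product type, and ETM 3 restricts menthol beyond cigarettes. Both deserve credit. But flavor preference describes what is bought when every flavor is available. ETM 3 comes last by design and keeps menthol e-cigarettes, and Section J sets out no comparison of it with ETM 1.

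Two stronger readings are tempting and not supported. A reader might infer that heavy ATP purchasing will be reported to FDA as caused by menthol ATPs; no planned analysis would produce that statement, so it is a prediction. A reader might also try to bound the effect by the menthol share of ATP purchases. The documents give no such share, and it would not be a valid bound. The outcome is milligrams of nicotine, so a buyer who loses a menthol product could switch to another and take home more.

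**Conclusion.** The point stands in a limited form. Menthol ATP availability does not vary across the 16 Visit 5 price trials, so its effect is not estimable from ETM 1 or from ETM 1 against ETM 2. No numerical size can be put on the unidentified effect from these documents. The conclusion rests only on the menus as C.6, Aim 3 and Section B describe them; it needs no assumption about sample size, variance or model.

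ETM 3 offers at most a partial answer, for the products from which it withdraws menthol, and only if there is no time or order effect between Visit 5 and day 30.

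A reader might infer that Aim 3 itself fails. It does not: the Visit 5 tasks do vary the cigarette offer, which is what Aim 3 is about. There is, however, an adjoining gap. J.4 names an outcome that depends on which cigarette is on offer, but its models run one cigarette type at a time, so no within-person ETM 1 against ETM 2 contrast is specified.

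**What to change.** 1. **Reword the sentence in C.6**, for example: *ETM 1 compared with ETM 2 shows how removing menthol VLNCs changes purchases when menthol ATPs remain on sale; it does not estimate the effect of menthol ATPs being available.* If ETM 3 is mentioned there, state that it always falls about 30 days later, so that it is confounded with time and order, and that it never removes menthol e-cigarettes. Before that, reconcile the Exploratory Aim (menthol kept in non-combustibles) with the 30-Day Follow-up section (menthol in e-cigarettes only).

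2. **Add to J.4** the within-person ETM 1 minus ETM 2 difference in ATP purchases, split by menthol against other flavors and by combustible against non-combustible. State the cigarette prices at which the tasks are compared, including the price of the non-menthol VLNC in ETM 2. This extends the flavor analysis in J.5 and addresses the nearest question the data can answer: whether people who lose menthol VLNCs move to menthol ATPs.

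The cost is one reworded sentence, one extra table from purchases already recorded, and a narrower stated conclusion. No new visit or task is needed.
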